Our overall research goal is to evaluate the clinical utility of preoperative pessary placement as a part of patient counseling or preparation for surgery. In this protocol we aim to increase patient preparedness for surgery, patient satisfaction, and post-operative quality of life in adult women scheduled for surgery for symptomatic pelvic organ prolapse. To accomplish this, following counseling regarding all treatment options for prolapse, we will perform a prospective case-crossover study where 112 subjects who elected for surgical management will utilize a pessary for 1-4 weeks prior to undergoing prolapse surgery.

We propose:

Specific aim 1a: To evaluate concordance of the Patient Global Impression of Improvement Score between vaginal pessary use (assessed prior to surgery) and surgical intervention (assessed at 3 months postoperatively) for women with pelvic organ prolapse. *Hypothesis:* There is a strong correlation between the self-reported Patient Global Impression of Improvement Score following pessary use and surgery, as assessed at 3 months post-operatively.

Specific aim 1b.) To evaluate concordance in symptomatic change in pelvic and voiding symptoms (measured by validated symptom questionnaires) from baseline between pessary use (assessed prior to surgery) and surgical intervention (assessed at 3 months postoperatively). *Hypothesis:* There is a strong correlation between the changes in pelvic and voiding symptoms following pessary use and surgery, as assessed at 3 months post-operatively

Specific aim 2: To evaluate the impact of preoperative pessary use on patient preparedness for surgery (measured by validated questionnaire) as compared between the initial office consultation and following 1-4 weeks of pessary use.

Hypothesis: Preoperative pessary use will increase self-reported preoperative patient preparedness for surgery compared to office counseling alone.

II. Research Strategy

1. Significance:

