The proposed project is a new approach to addressing the gaps in patient counseling and preparedness for surgery that currently exist. The proposed protocol will clarify the utility of pessary placement given the noted heterogeneity in current clinical practices. Additionally, while pessaries are at times used clinically to help differentiate potential symptoms that may improve with surgery, this is an empirical rather than evidence-based practice. Thus, correlation of symptomatic change in bladder, bowel or pain symptoms with pessary use and surgery is important for pre-operative counseling. Additionally, with recent evidence regarding the importance of preoperative patient preparedness on surgical outcomes and patient satisfaction, evaluating the use of a pessary as part of patient education and preoperative preparation may highlight a potential innovative, low-cost, low-risk, and widely accessible tool for improving patient care and obtaining the best experience for our patients.

C. Approach- Experimental Design and Methods:

C.1. Study design and overview

Overview: This is a single center, prospective, case-cross over trial of pessary use prior to reconstructive pelvic floor surgery for pelvic organ prolapse. The goal of the study is to evaluate the comparative efficacy of pessary use on pelvic floor symptoms versus surgical correction. Additionally, we will assess the impact that preoperative pessary use has on patient self-reported preparedness for surgery.

Study procedure and design: All patients will undergo baseline symptom evaluation via validated questionnaire at the time of their initial office consultation. Following this, the patient will undergo pessary fitting at least 7 days prior to scheduled surgical prolapse repair. The pessary will be left in place and symptomatic change from baseline assessed via validated questionnaire roughly 4 weeks after use or immediately prior to surgery (i.e. with the pessary in place). The pessary will then be removed at the time of surgery, and the patient will undergo surgical correction of their pelvic organ prolapse (including all restorative surgical procedures, abdominal and transvaginal). A concomitant anti-incontinence procedure will be performed at the discretion of the treating physician in consultation with the patient. The patient's symptomatic

outcome from surgery will then be reassessed by validated questionnaire at 6 weeks and 3 months postoperatively. (See Study Design Flow Chart)

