treatment (pessary and surgery): Pelvic Floor Impact Questionnaires (PFIQ-7),³⁷ Pelvic Organ Prolapse Distress Inventory 6 (POPDI-6),³⁷ and Overactive Bladder Symptom Score (OABSS).³⁸ Thus, questionnaire assessments will be completed at the time of initial consultation, immediately prior to surgery (after pessary use), at 6 weeks postoperatively during office consultation, and via mailed questionnaires and phone interviews at 3 months. Patient preparedness for surgery will be assessed via validated questions after completing the standard office based counseling and signing the surgical informed consent (prior to pessary use), as well as immediately prior to surgery (after pessary use), according to validated questions evaluating self-reported preparedness for pelvic surgery.² Furthermore, following treatment with a pessary (prior to surgery), at 6 weeks and 3 months after surgery patients will complete the Patient Global Impression of Improvement (PGI-I) question.^{1, 35} All adverse events associated with pessary use or surgery will be documented and abstracted.

Baseline characteristics for the patients included in the trial will be reported as median with inter-quartile range for continuous variables and counts with percentages for categorical variables. The percent concordant will be calculated along with the corresponding 95% confidence interval. Given the paired nature of the data (post-pessary vs. post-surgery), differences between the two time points for dichotomous responses will be assessed using McNemar’s test whereas differences between ordinal responses will be assessed using Bowker’s test for symmetry. The correlation between the two time points for summary scores from validated questionnaires (POPDI-6, PFIQ-7, OABSS) will be assessed using Lin’s concordance correlation coefficient. All calculated p-values will be two sided and will be considered significant if < 0.05.

Study Schedule	Initial visit	After pessary use, day of surgery	Surgery	6 wks after surgery (clinic visit)	3 mos after surgery (mailing)
Medical History and Physical	X				
Informed Consent	X				
Pessary Fitting	X				
Preparedness for Surgery	X	X			
PFIQ-7	X	X		X	X
POPDI-6	X	X		X	X
OABSS	X	X		X	X
PGII		X		X	X
Surgery			X		

C.6. Potential limitations of the study design and alternative strategies:

Potential Limitations:

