Carry-Over Effect: This would be encountered if preoperative pessary use changed the pelvic floor in a way that influenced the outcome of surgery. As there is no “wash-out” time from pessary removal to surgery, such an effect would impact the surgical outcome. Given that the pessary is a mechanical change in anatomy of the pelvic floor, we anticipate that with pessary removal there would not be residual impact from the pessary.

Recruitment: As patients would be counseled regarding surgery and pessary use and would have elected for surgery prior to study consent, we could encounter difficulties with recruitment in that patients would need to consent to temporary pessary use. Given the volume of patients seen in our department and the sample size needed, we feel that this should not be prohibitive.

Alternative strategies:

Observational cohort: An alternative strategy would be to compare symptomatic improvements between pessary use and surgery in two separate cohorts of patients, in an observational study. As there would be

significant selection bias in patients that undergo pessary placement rather than surgical correction, this methodology was not preferred.

Randomized clinical trial: A randomized clinical trial could be performed where patients are randomized to preoperative pessary use or proceeding directly to surgery. This approach could potentially minimize the impact of confounding variables. This method was not preferred due to perceived difficulty in recruitment (as patients may have a specific time in which they prefer to have surgery) and difficulty in surgical scheduling.

C.7. Timeframe: (24 months)

For Aim 1, we estimate that it will take 8 months for recruitment of the 62 patients, assuming a recruitment rate of 15% (~54 surgeries for prolapse in our division per month, as estimated by averaging volume from 2013 and 2014). For completion of Aim 2, we estimate that it will take 14 months to recruit the 112 patients for study, assuming a recruitment rate of 15%. Given the surgical volume in our division we anticipate being able to meet the accrual requirements.

	2016							2017											2018					
Study Month	1	2	3	4	5	6	7	8	9	10	11	12	13	14	15	16	17	18	19	20	21	22	23	24
Aim 1																								
Data Collection	x	x	x	x	x	x	x	x																
Data Analysis									x	x														
Manuscript										x	x	x	x											
Aim 2																								
Data Collection	x	x	x	x	x	x	x	x	x	x	x	x	x	x										

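### The Aim 2 hypothesis credits the pessary with a gain over office counselling, but the single-group before-after comparison can show only that preparedness changed

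*Combined protocol and SAP*

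**What the plan says.** Section I (Specific Aims) gives the Aim 2 hypothesis as "Preoperative pessary use will increase self-reported preoperative patient preparedness for surgery compared to office counseling alone". The aim statement just above it speaks of the impact of pessary use on preparedness, and defines the comparison as within-patient: "as compared between the initial office consultation and following 1-4 weeks of pessary use".

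Section C.1 describes the design: "This is a single center, prospective, case-cross over trial of pessary use prior to reconstructive pelvic floor surgery for pelvic organ prolapse". No group goes to surgery without a pessary, and the order is the same for everyone. After baseline assessment, "the patient will undergo pessary fitting at least 7 days prior to scheduled surgical prolapse repair".

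Section C.5 fixes the two preparedness measurements: "after completing the standard office based counseling and signing the surgical informed consent (prior to pessary use), as well as immediately prior to surgery". The study schedule agrees, with preparedness marked at the initial visit and on the day of surgery.

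Section C.3 calls preparedness the secondary aim and counts a woman as prepared only if she chooses the top category of a 6-point scale. Section C.4 sizes Aim 2 with a two-sided McNemar test (58% before, 75% after, correlation 0.30, 84 evaluable women, 112 consented). The 58% comes from an outside series of 79 women. Aim 2 therefore sets the trial's recruitment target.

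Section C.6 lists two limitations: carry-over of the pessary onto the surgical outcome, and recruitment. Under alternative strategies it describes a randomised trial of preoperative pessary against going directly to surgery and grants that this could reduce confounding, but adds: "This method was not preferred due to perceived difficulty in recruitment". It also cites surgical scheduling.

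**The concern.** The hypothesis asserts that the pessary adds something to counselling. To observe that, one would need to know how prepared the same kind of woman feels on the day of surgery when she has had counselling and no pessary. The plan never measures that state. It measures women just after counselling, and then again at least a week later with the pessary in place and surgery imminent. Pessary wear is fully confounded with the passage of time, the nearness of the operation and being asked the same question twice.

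The crossover label does not help here. A crossover protects against time effects when the order varies, or when there is an untreated interval with its own second measurement. Aim 2 has neither.

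If the plan is followed as worded, a significant McNemar result would be reported as a benefit of the pessary over counselling, and a null result as its absence. The abstract expects the trial to settle the clinical utility of routine preoperative placement, and section A.4 suggests that universal use could improve preparedness, so the wording of this conclusion matters.

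**Working it through.** **1. The plan's own figure.** Inputs from C.4: p1 = 0.58, p2 = 0.75, correlation 0.30, two-sided alpha 0.05, power 80%.

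- Both prepared: p11 = p1·p2 + 0.30·√[p1(1−p1)·p2(1−p2)] = 0.4350 + 0.30 × 0.2137 = 0.4991.
- Prepared before only: p10 = 0.58 − 0.4991 = 0.0809.
- Prepared after only: p01 = 0.75 − 0.4991 = 0.2509.
- Discordant: ψ = 0.3318. Difference: d = 0.17.
- Miettinen's formula: n = [1.960ψ + 0.8416·√(ψ² − d²(3+ψ)/4)]² / (ψd²) = [0.6503 + 0.2468]² / 0.00959 = 83.9, so 84.
- Drop-out: 84 / 0.75 = 112.

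Both stated figures reproduce. The arithmetic is not at fault.

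**2. What that calculation tests.** Its inputs are the two proportions in the same women, before and after. Under the null hypothesis p01 = p10, meaning no net change. Nothing in it stands for the day-of-surgery proportion without a pessary. If c is the change that would have happened anyway and e is the pessary effect, the test sees only c + e.

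**3. Illustration under assumed drift.** The documents give no value for c, so the values below are assumptions. With n = 84, p1 = 0.58 and correlation 0.30, let M be the number of discordant pairs, binomial(84, ψ), and B the number of upward pairs given M, binomial(M, p01/ψ). The uncorrected McNemar test is significant when (2B − M)²/M ≥ 3.841. Summing over all outcomes with B > M/2 gives:

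| Net change c + e | p2 | p10 | p01 | P(significant increase) |
|---|---|---|---|---|
| 0 points | 0.58 | 0.1705 | 0.1705 | 2.6% |
| +5 | 0.63 | 0.1431 | 0.1931 | 12.4% |
| +10 | 0.68 | 0.1165 | 0.2165 | 36.6% |
| +12 | 0.70 | 0.1061 | 0.2261 | 49.7% |
| +17 | 0.75 | 0.0809 | 0.2509 | 80.8% |

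With e = 0, the last column is the chance of crediting the pessary with a pure drift. The same rows cover drift in the other direction: a true pessary effect of 17 points with an assumed drift of −7 points has a net change of 10, so the chance of detecting it falls from 80.8% to 36.6%.

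The +17 row is the plan's own power with the effect relabelled as drift. The table shows that the test cannot tell the two apart. It does not show that drift exists.

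**The case against.** The strongest reply is that the plan is open about the contrast. The aim statement gives the within-patient timing, and C.5 places the first measurement after counselling and before the pessary. On that reading, counselling alone simply means the pre-pessary state of the same women, and the design does contain that comparison. This stands in part: a reader might infer that the plan hides its comparator or has none, and the documents do not support that. What remains is the causal reading. A before-after difference is described correctly in the aim and then claimed as an increase due to the pessary in the hypothesis.

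C.6 also names the controlled alternative, grants that it could reduce confounding, and gives reasons for declining it. That choice is defensible. But the acknowledgement is general. It does not say that preparedness may change without a pessary, and it leaves the hypothesis as worded.

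Three stronger inferences should be resisted:

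- **That other pre-surgical contact contaminates the comparison.** The schedule puts pessary fitting at the initial visit and shows no study visit between that and the day of surgery, so the documents give no basis for this.
- **That preparedness is likely to rise by itself.** Nothing in the documents says so. The interval may be as short as 7 days, and preparedness could fall.
- **That Aim 2 alone would carry a recommendation for routine use.** It is a secondary aim, and section A.3 ties universal use to agreement in symptom change between pessary and surgery.

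**Conclusion.** The point holds as a mismatch between claim and design. The Aim 2 analysis can estimate the change in the proportion who feel fully prepared, from the end of counselling to the day of surgery. It cannot attribute that change to the pessary, in either direction, and C.6 does not say so for Aim 2. This rests only on the documented design: one group, fixed order, two measurements.

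The size of any bias is unknown. The probabilities of 12% at 5 points and 37% at 10 points depend wholly on assumed upward drifts and illustrate the test's behaviour. They should not be read as an estimate of error in this trial. Nor is the sample size wrong: 84 and 112 are correct for a before-after change. Because failure to wear the pessary counts as drop-out in C.4, the pairs may also be limited to women who tolerated it, so the restated aim should refer to women who used a pessary.

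**What to change.** Restate the Aim 2 hypothesis and the planned conclusion as the change in the proportion giving the top preparedness response, from the end of office counselling to the day of surgery, among women who used a pessary. Remove the comparison with counselling alone and any wording that attributes the change to the pessary. Add to C.6 that this is an uncontrolled before-after comparison and that elapsed time, approaching surgery and repeat questioning could move preparedness either way.

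This needs no extra patients, visits or analyses, and leaves the sample size as it is. The price is a weaker claim for a secondary aim.

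Two larger remedies are not proposed. Using women who did not wear the pessary as a reference group would not work. At most 112 − 84 = 28 would be available, fewer in practice because the 25% also covers missing questionnaires, and they would be self-selected. With no change at 58% and correlation 0.30, the variance per pair is 2 × 0.58 × 0.42 × 0.70 = 0.341. The 95% half-width on their own change is 1.96 × √(0.341/28), about 22 points. On the difference from 84 wearers it is 1.96 × √(0.341/28 + 0.341/84), about 25 points. Both exceed the planned 17-point effect.

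A concurrent randomised control would supply the missing contrast, but at 58% against 75% it needs 120 evaluable women per arm, so 240 / 0.75 = 320 consented. At C.7's 15% of about 54 surgeries a month (8.1), that takes about 40 months, against the 14 months planned for recruitment.

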Prediction of postsurgical
symptomatic outcomes with
preoperative pessary use

NCT#02680145

08/22/2016

Prediction of postsurgical symptomatic outcomes with preoperative pessary use

Principal Investigator- [name]

Co-Investigator- [name]

Abstract

Pelvic organ prolapse is a highly prevalent and distressing condition for patients. Despite standard office-based consultation many patients report feeling unprepared for surgery. Likewise, in cases of equivocal symptoms, it is difficult to predict the ability of surgery to improve patient's quality of life and meet expectations. Occasionally, some providers utilize a pessary to evaluate the potential role for surgical correction. However, this is an empiric practice, rather than evidence-based. In addition to the evaluation of symptomatic improvement, pessary use in this setting is an important consideration as it may provide a better functional demonstration of the expected postoperative quality of life, compared to office-based discussion. The purpose of this project is to evaluate the potential role of routine pessary placement prior to planned surgery for symptomatic prolapse in a prospective case-crossover trial where patients scheduled for operative prolapse repair will utilize a pessary preoperatively. We anticipate that this trial will define the clinical utility of routine preoperative pessary placement, and by shaping patient expectations and increasing preparedness for surgery, we anticipate improving satisfaction and quality of life.

Research Plan

I. Specific Aims:

Pelvic organ prolapse is a highly prevalent issue in adult women and can have a large impact on a woman's quality of life, leading to discomfort, decreased energy and increase social isolation. Notably, the prevalence of prolapse increases with advancing age and it is estimated that the lifetime risk of a woman undergoing surgery for bothersome prolapse is as high as 13%. Likewise, given the present age distribution in the United States, the number of women seeking treatment for this issue in the future will continue to expand. While many women will undergo surgery, preoperative counseling in preparation for surgery is variable. In fact, self-reported patient preparedness for prolapse surgery has been reported as low as 58% in a previous series from a large tertiary care center. This is an important consideration as patient preparedness for surgery is associated with patient satisfaction and symptomatic improvement.

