C.2. Participants

Study population: The study will be open to women (over age 18) presenting for evaluation and management of symptomatic pelvic organ prolapse at Mayo Clinic (Rochester, MN), who elect to undergo surgical management.

Inclusion criteria: Female patients: 1) older than 18 years of age; 2) with symptomatic pelvic organ prolapse; 3) electing for surgical repair of pelvic organ prolapse (transvaginal or transabdominal) at least 7 days after office consultation. A minimum of one week was chosen as the duration of pessary use, as this was found sufficient in a study evaluating diagnosing occult urinary incontinence with pessary use prior to prolapse surgery;³⁶ 4) who understand and have signed written informed consent for preoperative pessary placement.

Exclusion criteria: Patients that: 1) have previously been managed with a pessary for pelvic organ prolapse; 2) patients undergoing obliterative prolapse surgery (i.e. Colpocleisis), 3) are scheduled for surgery for pelvic organ prolapse less than 7 days after office consultation 4) have an isolated rectocele; 5) have allergies to both latex and silicone; 6) have an active pelvic infection.

C.3. Outcome Assessment

The primary aim (1a) will be assessed using the 7-point Likert scale of the Patient Global Impression of Improvement (PGI-I).^{1, 35} Concordance will be estimated along with a 95% confidence interval. Patient's will be considered treatment success if they answer "much better" or "very much better" on the PGI-I scale.³⁵ The additional primary aim (1b) will be assessed using Lin's concordance correlation coefficient for responses to: Pelvic Organ Prolapse Distress Inventory-6 (POPDI-6) which measures prolapse symptom severity, Pelvic Floor Impact Questionnaire-7 (PFIQ-7) to evaluate patient bother from their bladder/vaginal/bowel symptoms, and the Overactive Bladder Symptom Score (OABSS). The secondary aim will be assessed by evaluating patient responses to a preoperative preparedness questionnaire. Patients will be considered prepared for surgery if they answer "strongly agree" on a 6-point Likert scale, with responses ranging from "strongly disagree" to "strongly agree" to the question: "Overall, I feel prepared for my upcoming surgery."²

C.4. Sample Size Considerations

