Aim 1: Using the 7-point Likert scale of the PGI-I, we anticipate an overall concordance of at least 80% between the within patient ratings following pessary use and 6-weeks following surgery after collapsing the categories into a) much better or very much better, b) a little better, no change, or a little worse, or c) much worse or very much worse. In order to estimate the concordance with a ½ width of the 95% CI of 10% (i.e. 95% CI of 70.8-90.5%), the study will need 62 patients.

Aim 2: Based on a recent study of 79 women who underwent reconstructive pelvic surgery after standard office counseling, 58% strongly agreed that they were prepared for their upcoming surgery.² If we assume that following pessary use, 75% will endorse that they strongly agreed that they were prepared for their upcoming surgery, then the study will have 80% power to detect this difference with a sample size of 84 patients. This calculation was based on two-sided McNemar's test for comparing correlated proportions assuming a mild correlation (0.30) between the paired measures and a type I error of 0.05. Assuming a conservative 25% drop-out rate (failure to wear the pessary or complete follow-up questionnaires) then the study would need to consent 112 patients.

Feasibility: The Division of Urogynecology at Mayo Clinic, Rochester, MN typically performs roughly 1350 surgeries annually (averaged from surgical volume from 1/1/2013 to 1/1/2015). Among those, the four fellowship trained Urogynecologists typically perform roughly 650 prolapse procedures per year. Thus, given the large surgical volume, recruitment for this study is feasible as a single center trial.

C.5. Data Collection

Preoperative demographic data, complete medical and surgical histories, as well as current medications and allergies will be obtained to ensure patients meet inclusion and exclusion requirements. Participants will fill out the following validated questionnaires and questions prior to any intervention and following each

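### Lin's coefficient suits Aim 1b's concordance objective, but as the only analysis of the symptom scores it cannot separate poor prediction from a larger average benefit of surgery

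*Combined protocol and SAP*

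**What the plan says.** The title of the study is "Prediction of postsurgical symptomatic outcomes with preoperative pessary use". In I. Specific Aims, the Aim 1b objective is "To evaluate concordance in symptomatic change in pelvic and voiding symptoms" from baseline, comparing pessary use with surgery at 3 months. The hypothesis under the same aim is worded differently: "There is a strong correlation between the changes in pelvic and voiding symptoms following pessary use and surgery".

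C.3 calls Aim 1b an additional primary aim and assesses it with Lin's "concordance correlation coefficient for responses to" POPDI-6, PFIQ-7 and OABSS. C.5 says that "The correlation between the two time points for summary scores from validated questionnaires" will be assessed with the same coefficient.

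The other paired methods in C.5 are for other data. McNemar's test is for dichotomous responses, and "differences between ordinal responses will be assessed using" Bowker's test. Percent concordance serves the PGI-I. For the three summary scores the plan contains no regression, no Pearson or Spearman coefficient and no paired mean difference, although C.1 gives the study goal as to "evaluate the comparative efficacy of pessary use on pelvic floor symptoms versus surgical correction". No value of the coefficient is named as strong.

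**The concern.** Lin's coefficient equals the Pearson correlation multiplied by a factor that falls below 1 whenever the two measurements differ in mean or in spread. A single low value therefore has two quite different explanations. The women who do well with the pessary may not be the ones who do well after surgery. Or they may be the same women, with surgery giving more relief on average. The first says that a pessary trial does not predict the surgical result. The second says that it does, once the average difference is allowed for.

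A difference in means or spread cannot be ruled out from the protocol. I. Specific Aims says that the comparative degree of anatomic improvement is not well studied. The pessary scores are taken with the device in place after 1-4 weeks, and the surgical scores at 3 months. C.1 also allows a concomitant anti-incontinence procedure at surgery. At stake is whether the results of this aim can be read as an answer to the question in the title.

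**Working it through.** **The plan's own figures.** No figure is given for Aim 1b. The Aim 1 sample size in C.4 rests on PGI-I concordance and reproduces: 1.96² × 0.80 × 0.20 / 0.10² = 61.5, so 62 patients, and 50/62 has a Wald 95% CI of 70.8-90.5%, as stated. It does not depend on the symptom scores, so this point leaves it unchanged.

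**Inputs for Aim 1b.** The documents give no mean, SD or correlation for POPDI-6, PFIQ-7 or OABSS. The values of r, u and v below are assumptions.

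**Formula.** Let r be the Pearson correlation, u the mean difference divided by the geometric mean of the two SDs, and v the ratio of the SDs. Then

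Lin's coefficient = r × 2 / (v + 1/v + u²),

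which for equal SDs (v = 1) is 2r / (2 + u²).

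**Results with equal SDs.**

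| assumed r | u = 0 | u = 0.5 | u = 1 |
|---|---|---|---|
| 0.70 | 0.70 | 0.62 | 0.47 |
| 0.80 | 0.80 | 0.71 | 0.53 |
| 0.90 | 0.90 | 0.80 | 0.60 |
| 1.00 | 1.00 | 0.89 | 0.67 |

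For example, r = 0.80 and u = 0.5 give 1.6 / 2.25 = 0.71, and u = 1 gives 1.6 / 3 = 0.53. Even perfect linear prediction gives 0.67 at u = 1. Unequal spread has the same kind of effect: r = 0.80, u = 0 and v = 2 give 0.80 × 2 / 2.5 = 0.64.

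A simulation with 84 patients and a true r of 0.80 gave mean Lin coefficients of 0.79, 0.70 and 0.53 at u = 0, 0.5 and 1. The mean Pearson correlation stayed at 0.80 throughout.

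**Scores or changes.** The aim speaks of change from baseline, while C.3 and C.5 speak of responses and summary scores. The point holds on either scale. With B, X and Y the baseline, post-pessary and post-surgery scores, (Y − B) − (X − B) = Y − X, so the mean difference is the same. Only the SDs and r differ.

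**Why not simply add the correlation of the changes.** Both changes subtract the same B. If B, X and Y are independent with common variance σ², then Cov(X − B, Y − B) = σ² and each change has variance 2σ², so the correlation is σ² / 2σ² = 0.50 although X says nothing about Y. Lin's coefficient computed on changes carries the same shared term.

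Adjusting for B removes this artefact: in that example the slope of Y on X given B is zero. The hypothesis about changes is not lost either. Y − B = a + b(X − B) + cB rearranges to Y = a + bX + (1 + c − b)B, so the adjusted slope b is the same for scores and for changes.

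**Precision of the added estimate.** For a partial correlation with one covariate, the Fisher-z half-width is 1.96 / √(n − 4). For an assumed partial correlation of 0.80 the 95% CI is 0.69-0.88 at n = 62 (half-width 0.257 around 1.099) and 0.71-0.87 at n = 84 (half-width 0.219).

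**The case against.** The strongest reply is that the method matches the objective. Aim 1b sets out to evaluate concordance, and that is what Lin's coefficient measures. Section A.3 asks whether improvement with a pessary mirrors that of surgery, and A.4 presents the pessary as a demonstration of the functional result. If surgery gives much more relief, the pessary has not demonstrated that result, and a coefficient that falls is doing its job. The document also uses the word correlation loosely. The Aim 1a hypothesis uses it too, yet Aim 1a is analysed by percent concordance, and C.5 describes Lin's coefficient itself as assessing correlation.

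This stands as far as it goes. A reader might infer that Lin's coefficient is the wrong choice and should give way to a Pearson correlation of changes. The documents do not support that: agreement is a stated target, and the shared baseline makes the unadjusted correlation of changes a poor test.

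It is also true that the size of the mean shift is assumed. The only stated expectation of similar response is PGI-I concordance of at least 80%, in C.4. That is a different measure, but it does not suggest a gap of 1 SD.

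What the reply leaves unanswered is the title. Concordance and prediction are different questions, and no planned analysis of these scores addresses the second or would explain a low value on the first.

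**Conclusion.** The point holds as a gap in the plan, not as an error in the chosen coefficient. Lin's coefficient is valid for the Aim 1b objective. On its own it neither isolates the association that the hypothesis asserts nor answers the prediction question. A low value could not be told apart from good prediction with a larger average benefit of surgery.

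That a mean or spread difference lowers the coefficient at a given positive correlation follows from the formula. How far it would fall in this trial cannot be computed from the documents: 0.71 and 0.53 illustrate r = 0.80 with equal SDs and shifts of 0.5 and 1 SD.

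A reader might go further and infer that a useful pessary test would be declared unhelpful. The plan does not say that. It sets no cut-off for the coefficient and ties no decision to Aim 1b. The risk is a result that cannot be interpreted. The sample sizes are unaffected.

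**What to change.** In C.3 and C.5, keep Lin's coefficient with a 95% CI as the concordance measure, and state whether it is computed on scores or on changes. Beside it, for each of POPDI-6, PFIQ-7 and OABSS, report:

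- the paired mean difference between pessary and surgery, with 95% CI;
- the association of the 3-month post-surgery score with the post-pessary score, adjusted for the baseline score, as a regression slope or partial correlation with 95% CI. Name this as the prediction result.

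Do not use the unadjusted Pearson or Spearman correlation of changes from baseline as the hypothesis test. If it is shown, label it descriptive and note the shared baseline.

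The cost is a longer results table and more estimates per score to interpret. The C.5 schedule already collects all three questionnaires at baseline, after pessary use and at 3 months, so no visits or patients are added.
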